## 4.4. Exploratory Endpoints Analysis

### 4.4.1.1. Definition of Endpoints

Exploratory endpoints include the following:

#### Part A

##### ELISA Results

GMT of total binding IgG antibodies against the SARS-CoV-2 index virus at 2 weeks after trial vaccination in subsets of each Part A cohort.

Geometric mean fold increases, from baseline to post-baseline time points after trial vaccination, in total binding IgG antibodies against the SARS-CoV-2 index virus in subsets of each Part A cohort.

##### Neutralizing Antibody Results

Geometric mean fold increases, from baseline to post-baseline time points after trial vaccination, in neutralizing antibodies against the SARS-CoV-2 index virus and against the SARS-CoV2 VOCs circulating at the time of the trial.

GMT of neutralizing antibodies against the SARS-CoV-2 index virus and the SARS-CoV-2 VOCs circulating at time of the trial, at 1, 4, 13 and 26 weeks after trial vaccination in subsets of each Part A cohort.

#### Part B

##### ELISpot Results

Geometric means of SARS-CoV-2-specific T cells secreting interferon- $\gamma$  / interleukin-4 at 1 week after ABNCoV2 vaccination within the immunogenicity subsets of each Part B cohort.

#### **4.4.1.2. Main Analytical Approach**

Geometric means and their corresponding 95% CIs will be used to summarize total IgG binding antibodies measured by ELISA in a subset of Part A subjects by cohort, vaccination arm, and time point. Age and baseline total IgG binding antibody results will be included as covariates in the model to compare the vaccination arms. The LS Means and 95% CIs from the model will be back transformed to their original scale. The difference between the ABNCoV2 and Comirnaty vaccination arms in the Part A cohorts, with respect to total IgG binding antibody results, will be described using the ratio of the GMTs (ABNCoV2 vs. Comirnaty) and corresponding 95% CIs, within each cohort, from the same model.

Cellular immune responses including SARS-CoV-2 specific T cells secreting interferon- $\gamma$  and interleukin-4 measured by ELISpot in subsets of both Part B cohorts will also be summarized using geometric means and 95% CIs.

Fold increases, defined as post-baseline result divided by the baseline result, for Part A ELISA results and Part B ELISpot results will be summarized by trial part, assay, cohort, vaccination arm (for Part A ELISA only), and time point. Geometric mean fold increases and corresponding 95% CIs will also be calculated.

The Part A ELISA results as well as the Part B ELISpot results will also be plotted as GMTs/GMSFUs and CIs over time for each assay, cohort, and vaccination arm (Part A ELISA) on the  $\log_{10}$  scale.

The combined cohort analyses will be similar to the analyses performed for each cohort.

Durability of neutralizing antibody results at 3 months and 6 months will be analyzed within the corresponding kinetics analysis set (Section 3) using GMTs, fold increases, and 95% CIs. These will be produced for subjects who are in the IAS for the primary endpoint analysis and provide serum samples at the 3 month or 6 month follow up visits, respectively. Both tables and figures will be presented by time point starting with baseline.

#### **4.4.1.3. Sensitivity Analyses**

There are no sensitivity analyses for the exploratory endpoints.

#### **4.4.1.4. Supplementary Analyses**

There are no supplementary analyses planned for the exploratory endpoints.

#### **4.4.1.5. Subgroup Analyses**

For the summaries of total IgG antibody response by ELISA, the same subgroup analyses performed for the primary estimand analysis in Section 4.2.5 will be presented for Part A.

### **4.5. Safety Analyses**

#### **4.5.1. Extent of Exposure**

Exposure to trial vaccine will be presented as the number of subjects receiving the trial vaccine within trial part, cohort, and vaccination arm (for Part A). The number and percentage of subjects

returning memory aids for the Safety Analysis Set will also be presented. All exposure and diary data will be listed.

#### **4.5.2. Adverse Events**

An AE is defined as any untoward medical event occurring after a subject has signed the informed consent form; it does not necessarily have a causal relationship associated with the administration of the trial vaccine.

##### **4.5.2.1. Serious Adverse Events**

A serious adverse event (SAE) is defined as any untoward medical occurrence that:

- Results in death,
- Is life-threatening,
- Requires in-patient hospitalization or prolongation of existing hospitalization,
- Results in persistent or significant disability or incapacity,
- Results in a congenital anomaly or birth defect, and/or
- Is an otherwise important medical event.

The criteria for an event being serious will be captured in the AE eCRF as reported by the investigator.

##### **4.5.2.2. Causality**

Relationship of the trial vaccine to the AE is assessed by the investigator using the categories “none”, “unlikely”, “possible”, “probable”, and “definite.” An AE assessed as possibly, probably, or definitely related will be counted as a related AE for the purpose of reporting. AEs categorized as none or unlikely related will not be considered related to trial vaccination. All AEs without a causality assessment from the investigator will preliminarily be classified as “possible”.

##### **4.5.2.3. Adverse Events of Special Interest**

Adverse events of special interest (AESIs) are generally defined as AEs that meet the following criteria:

- Known association with immunization or a specific vaccine platform;
- Theoretical association based on animal models;
- Occurrence during wild type disease as a result of viral replication and/or immunopathogenesis.

AESIs for ABNCoV2-03 are defined per Section 11.9 of the clinical trial protocol. An AE cannot be considered an AESI unless it occurs after the trial vaccination. For analyses, the investigator flagging of the AESI in the eCRF will be used to define AESIs.

#### 4.5.2.4. Medically Attended Adverse Events

Medically attended AEs (MAAEs) are defined as AEs with medically attended visits that were not routine visits for physical examination or vaccination, such as visits for hospitalization, an emergency room visit, or an otherwise unscheduled visit to or from medical personnel (medical doctor) for any reason. MAAEs for non-serious AEs are flagged on the eCRF. SAEs requiring hospitalization are also considered MAAEs for analysis purposes.

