Examples of such events are intensive treatment in an emergency room or at home for allergic bronchospasm; blood dyscrasias or convulsions that do not result in hospitalization; or development of drug dependency or drug abuse.

AESIs are generally defined as AEs that meet the following criteria:

- Known association with immunization or a specific vaccine platform;
- Theoretical association based on animal models;
- Occurrence during wild type disease as a result of viral replication and/or immunopathogenesis.

AESIs for this trial are defined as per Section 11.9.

Bavarian Nordic

ABNCoV2		Clinical Trial Protocol
ABNCoV2-03	Edition 8.0	

All AEs are collected from signing of ICF but should not be considered by the investigator to be an AESI unless occurring since receipt of trial vaccination.

MAAEs are defined as adverse events with medically attended visits that were not routine visits for physical examination or vaccination, such as visits for hospitalization, an emergency room visit, or an otherwise unscheduled visit to or from medical personnel (medical doctor) for any reason.

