11.9.2 Myocarditis and Pericarditis

Myocarditis and pericarditis are a subset of AESIs of particular interest. Postmarketing data from mRNA vaccine recipients have demonstrated increased risks of myocarditis and pericarditis in males under the age of 40 years following a second dose of mRNA vaccine. Cases have been reported in older males and in females as well, and also following other doses. Available data from short-term follow-up suggest that most individuals have had resolution of symptoms with conservative management, although information is not yet available about potential long-term sequelae.

The spike (S) protein antigen can induce antibodies to SARS-CoV-2 spike glycoproteins that cross-react with myocardial contractile proteins, including myocardial α -myosin heavy chain (Vojdani and Kharrazian, 2020). In contrast to the currently licensed COVID-19 vaccines, the ABNCoV2 candidate vaccine does not contain the full-length S protein of the SARS-CoV-2 virus, but specifically the receptor binding domain (RBD) of the S protein. However, as the pathomechanism for myocarditis or pericarditis following COVID-19 vaccination is not fully understood, and the specific role of the RBD remains unclear, precautionary measures will be implemented for this trial.

Symptoms of myocarditis or pericarditis include chest pain, shortness of breath, or feelings of having a fast-beating, fluttering, or pounding heart, with onset of symptoms most commonly reported within a few days following vaccination. While some cases required intensive care support, available data from short-term follow-up suggest that symptoms resolve in most individuals with conservative management. Information is not yet available about potential long-term sequelae. Subjects will receive educational materials explaining the symptoms of

Bavarian Nordic

ABNCoV2-03

Edition 8.0

myocarditis and pericarditis and instructing them to seeking medical attention if they occur. Subjects reporting acute chest pain, shortness of breath, palpitations, or other signs or symptoms of myocarditis or pericarditis within 4 to 6 weeks after vaccination will be referred to a cardiologist for evaluation and management. Cases of myocarditis and pericarditis will be followed until resolution of symptoms and abnormal test findings.

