Determination of myocarditis and pericarditis will be performed based on the case definitions and guidelines from the Brighton Collaboration Myocarditis/Pericarditis Working Group (Sexson Tejtel et al., 2022). Reference to the publication of these case definitions is provided in Appendix 3. Cases of myocarditis or pericarditis occurring in temporal association with vaccination will be considered as potentially related, unexpected, and serious (as important medical events, even if other seriousness criteria are not met). These will be included in expedited reporting for the trial.

An adverse event follow-up questionnaire for cardiac events (Appendix 4) will be used during the study.

The DMC will review cases of myocarditis and pericarditis, with details as to the timelines for review and ad-hoc meetings to be described in the DMC charter (Section 13.3.1). In addition, recommendations for pausing or halting the trial will be in line with the stopping rules described in Section 13.3.2.

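### SAP 4.5.2.4 gives no route into the MAAE counts for a serious event that was medically attended without hospital admission, although its own definition includes such events

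*SAP*

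**What the plan says.** Protocol 11.1.5 sets the definition: "MAAEs are defined as adverse events with medically attended visits that were not routine visits for physical examination or vaccination", with the examples "such as visits for hospitalization, an emergency room visit, or an otherwise unscheduled visit to or from medical personnel (medical doctor) for any reason". Seriousness plays no part in it. SAP 4.5.2.4 opens with the same definition.

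The SAP section then gives two ways in which an event becomes an MAAE in the analysis, the first for non-serious events and the second for serious ones: "MAAEs for non-serious AEs are flagged on the eCRF. SAEs requiring hospitalization are also considered MAAEs for analysis purposes".

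No route is stated for an SAE that was medically attended without admission.

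SAP 4.5.2.6 uses the resulting variable in three places. The Active Trial Phase tables by SOC and PT have an MAAE entry with related MAAEs beneath it. The overall summary has an MAAE line for solicited and unsolicited events together, and another for unsolicited events.

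**The concern.** The definition is wider than the derivation. A programmer who follows the two routes as written would count a non-serious event that led to an emergency room visit, but not a serious event that led to the same visit without admission. The stand-alone MAAE and related-MAAE rows would then be too low, and the missing events would be serious ones.

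The class matters because it can include cases that the protocol watches closely. Protocol 11.9.2 singles out myocarditis and pericarditis, treats them as serious by rule, and sends symptomatic subjects to a cardiologist. That section also notes raised risks after mRNA vaccines, and the Part A comparator is an mRNA vaccine. Any omitted events therefore need not be balanced between the arms, and the documents do not show which way an imbalance would go.

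**Working it through.** No arithmetic applies: the documents give no rate of MAAEs, or of SAEs without admission, for this trial. The check sets the definition against the two routes and asks which attended events neither one catches.

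**Step 1. Classify each kind of event under SAP 4.5.2.4 as written.**

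| Event | Meets the definition | eCRF flag route (described for non-serious AEs) | Hospitalization route (SAEs) | In MAAE rows | In SAE rows |
|---|---|---|---|---|---|
| Non-serious AE, emergency room or unscheduled doctor visit | Yes | Yes | Not applicable | Yes | No |
| SAE, admitted to hospital | Yes | Not described | Yes | Yes | Yes |
| SAE, emergency room or outpatient doctor, not admitted | Yes | Not described | No | **No** | Yes |
| SAE, no medical visit | No | Not described | No | No | Yes |

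Only in the third row does the result disagree with the definition.

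**Step 2. Ask whether the third row is a real class.** Four places in the documents say that it is.

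- Protocol 11.1.5 gives as examples of important medical events that are usually considered serious: "intensive treatment in an emergency room or at home for allergic bronchospasm; blood dyscrasias or convulsions that do not result in hospitalization". The emergency room case is a qualifying visit without any need for admission. The other examples show that an SAE need not involve admission, but they do not say that a visit took place.
- For myocarditis or pericarditis linked in time to the vaccination, Protocol 11.9.2 says that cases "will be considered as potentially related, unexpected, and serious (as important medical events, even if other seriousness criteria are not met". Under the same section, subjects with suggestive symptoms within 4 to 6 weeks "will be referred to a cardiologist for evaluation and management". A case handled in that way without admission is both serious and medically attended.
- SAP 4.5.4 leaves out of the vital-signs analysis the Grade 4 categories that require an emergency room visit or hospitalization, because those events should be reported as SAEs. The SAP thus expects some SAEs to rest on an emergency room visit.
- Protocol 11.14.2 provides for an MAAE that is also serious, and attaches no hospitalization condition.

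**Step 3. Trace the outputs.**

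- Affected: the MAAE entry and the related-MAAE entry in the Active Trial Phase tables, and the two MAAE lines in the overall summary (all SAP 4.5.2.6).
- Not affected: SAE and related-SAE rows, the SAE listing, and the AESI rows and listing where the event is an AESI. Myocarditis and pericarditis are AESIs under Protocol 11.9.2.
- Not affected if analysed as a union: the protocol endpoint of SAEs, AESIs or MAAEs (Protocol 5.3, SAP Table 1), because the event enters as an SAE. SAP 4.5.2.6 does not, however, list a table of that union.

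**Step 4. Look for a declared change.** SAP Section 1 says that deviations from the protocol are described in Section 4.8. Section 4.8 does not mention MAAEs, so the narrower count is not presented as a deliberate change.

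**The case against.** The strongest reply is that the SAP never says that hospitalized SAEs are the sole serious events to be counted. The section opens with a definition that has no seriousness limit, and the hospitalization sentence adds events and removes none. Protocol 11.14.2 requires all MAAEs to be entered in the eCRF and allows for serious ones. If the flag can be set for an SAE, nothing is lost. The analyses are also descriptive, the same rule applies to both arms, and no event disappears from the report.

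Most of this stands. A reader might infer that the SAP excludes every SAE without admission. The documents do not support that: the exclusion follows only because no other route is stated, and it depends on an eCRF that is not in the documents. What remains is that the SAP describes the flag for non-serious events only, so its derivation does not deliver its own definition.

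Three further inferences also go too far:

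- *That the rule removes the more serious attended events in general.* Hospitalized SAEs are expressly kept; only those without admission are in doubt.
- *That a stand-alone MAAE endpoint is understated.* In the current text of Protocol 5.3 the endpoint is the composite of SAEs, AESIs or MAAEs. Related MAAEs are not a protocol endpoint, and they appear in one list of SAP 4.5.2.6 only.
- *That about 3 subjects would be lost, from 0.1% of 3000 = 0.001 × 3000 = 3.* The 0.1% in Protocol 12.2.2 and SAP 5.2 is the incidence of an AE that 3000 subjects would allow the trial to detect. It is not a rate of attended SAEs without admission, and the documents give no such rate.

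**Conclusion.** The point holds as an inconsistency between a definition and its derivation. Followed as written, SAP 4.5.2.4 leaves a medically attended SAE without admission out of the MAAE rows, and out of the related-MAAE row where the event is related.

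This rests on one assumption that the documents cannot settle: that the eCRF flag is available for non-serious events only, as the SAP describes it. If the flag can also be set for SAEs, the counts may be right and only the SAP wording needs correcting.

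The effect is confined to the stand-alone MAAE and related-MAAE results. The number of events cannot be estimated from the documents and is probably small. No safety event is hidden, because each one still appears among the SAEs, and among the AESIs where it qualifies. The change is still worth making: the class is foreseen in both documents and can include myocarditis and pericarditis, and the correction costs very little.

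**What to change.** Replace the last sentence of SAP 4.5.2.4 with: *SAEs with any qualifying medically attended visit (hospitalization, emergency room or unscheduled physician visit) are also MAAEs for analysis.* State the source as well: the eCRF flag if it can be set for SAEs, otherwise the SAE data. If neither records the visit, review the non-hospitalized SAEs blinded before unblinding and assign MAAE status then. The data review meeting in SAP 4.7 is a natural place for this. SAEs from the follow-up phase of Part A should go to staff who are still blinded at subject level (SAP 4.1.3).

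Apply the rule to every MAAE and related-MAAE row in SAP 4.5.2.6. If the sponsor means to keep the narrower count, Section 4.8 should say so and the row labels should match.

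The cost is one extra derivation, or a short review of a few SAEs. Counting every SAE as an MAAE would be simpler, but it departs from the visit-based definition and would over-count any SAE without a visit, so review is the better fallback.

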#### 4.5.2.5. Solicited Adverse Events

Solicited AEs are defined as all symptoms specifically listed in the memory aid provided to the subjects following vaccination. After vaccination, the subjects are requested to monitor and record local symptoms (i.e., erythema, swelling, induration, pruritus and pain at the injection site) as well as general symptoms (i.e., body temperature increase/pyrexia, headache, chills, myalgia, nausea and fatigue) in the memory aid daily for the day of vaccination and the following 7 days (Days 1 to 8, an 8-day period). If symptoms persist at Day 8, daily symptoms and temperatures will be documented each day until resolved. Solicited AEs that meet the criteria for SAEs will be documented in the AE eCRFs.

There will be 2 sets of grading for solicited local (Table 6) and general (Table 7) AEs. Memory aids for solicited AEs were reviewed and collected using the Bavarian Nordic (BN) standard grading scale, but in an effort to align with the FDA's *Guidance for Industry: Toxicity Grading Scale for Healthy Adult and Adolescent Volunteers Enrolled in Preventive Vaccine Clinical Trials*, events that were collected in millimeters (mm) or degrees (°) will be mapped to the FDA grading scale for the primary analysis of solicited AEs. Grading using the BN standard grading scale will also be presented as a sensitivity analysis to compare to the FDA grading scale analysis and to prior trial results. In the grading tables for solicited AEs, the primary analysis scale using the FDA grading is labeled "Grading for Analyses" and the historical BN standard grading scale is labeled "Grading Assessed at Diary Review."

#### Solicited Local AEs

Occurrence, intensity, and duration of solicited local AEs during the 8-day period after vaccination will be summarized for each vaccination arm within cohorts and combined cohorts. Note, solicited local AEs are always assumed to be related to vaccination so no summaries based on causality will be performed.

Injection site erythema, swelling, and induration will be measured using a provided ruler, and the maximum diameter will be recorded for each day on the memory aid. The intensity for these symptoms will be graded as follows:

**Table 6: Solicited Local Event Grading**

	Grading for Analyses		Grading Assessed at Diary Review	
	Grade	Severity Measure a	Grade	Severity Measure
Injection site erythema, Injection site swelling, and Injection site induration b (longest diameter)	0	0 cm	0	0 mm
	1	2.5 - 5.0 cm	1	<30 mm
	2	5.1 – 10 cm	2	≥30 – <100 mm

	3	> 10 cm	3	≥100 mm
Injection site pruritus	Same as assessed at diary review		0	Absent
			1	Mild
			2	Moderate
			3	Severe
Injection site pain	Same as assessed at diary review		0	Absent
			1	Pain on touch
			2	Painful when limb is moving
			3	Spontaneously painful/prevents normal activity

aPer FDA “Guidance for Industry: Toxicity Grading Scale for Healthy Adult and Adolescent Volunteers Enrolled in Preventive Vaccine Clinical Trials”, September 2007. Available at <https://www.fda.gov/media.73679/download>.

Note, values measured in cm between 0 and 2.5, exclusive, will be assigned a grade of 0.

bPer FDA guidance, injection site swelling, and induration are combined into one scale (i.e., injection site swelling/induration).

### Solicited General AEs

Occurrence, relationship, intensity, and duration of solicited general AEs during the 8-day period after vaccination will be summarized for each vaccination arm within cohorts and combined cohorts based on the grades defined below:

**Table 7: Solicited General Event Grading**

MedDRA coded Preferred Term	Grading for Analyses		Grading Assessed at Diary Review	
	Grade	Severity Measure a	Grade	Severity Measure
Body temperature (oral) b	0	<38.0°C (<100.4°F)	0	< 37.5°C (< 99.5°F)
	1	38.0 – 38.4°C (100.4 – 101.1°F)	1	≥ 37.5 – < 38.0°C (≥99.5 – <100.4°F)
	2	38.5 – 38.9°C (101.2 – 102.0°F)	2	≥ 38.0 – < 39.0°C (≥100.4 – <102.2°F)
	3	39.0 – 40.0°C (102.1 – 104.0°F)	3	≥ 39.0 – < 40.0°C (≥102.2 – <104.0°F)
	4	>40.0°C (>104.0°F)	4	≥ 40.0°C (≥ 104.0°F)
Headache, Myalgia, Nausea, Chills and Fatigue	Same as assessed at diary review		0	None
			1	Mild: easily tolerated, minimal discomfort and no interference with daily activity

			2	Moderate: Some interference with daily activity
			3	Severe: Prevents daily activity

aPer FDA “Guidance for Industry: Toxicity Grading Scale for Healthy Adult and Adolescent Volunteers Enrolled in Preventive Vaccine Clinical Trials”, September 2007. Available at <https://www.fda.gov/media/73679/download>.

bPyrexia is defined as oral temperature  $\geq 38.0^{\circ}\text{C}$  ( $\geq 100.4^{\circ}\text{F}$ ), which is fever Grade  $\geq 1$  by FDA grading and oral temperature Grade  $\geq 2$  as assessed at diary review.

Causal relationship between solicited general AEs and the vaccine will be assessed by the investigator as described in Section 4.5.2.2.

